We have thus far treated 70 patients on the vidaza + nivolumab trial for relapsed/refractory AML as of Dec 30 2016 (Daver N, Sharma P et al., American Society of Hematology, 2016 abstract #763). The RP2D of 5-azacytidine and nivolumab was established as 5-azacytidine 75mg/m² days 1-7 and nivolumab 3.0 mg/kg on days 1 and 14 of each cycle in the ongoing clinical trial. 0/6 patients experienced a DLT at this dose during the safety-run-in phase. All subsequent 47 patients have received this RP2D dose of 5-azacytidine and nivolumab. 51 patients have completed at least 3 cycles and are evaluable for response and toxicity. 51 pts with a median age of 69 years (range, 45 – 90), secondary AML (55%), poor risk cytogenetics (47%), median number of prior regimens 2 (range, 1-7) have been enrolled. All 51 pts had baseline next generation sequencing and most frequently detected mutations included *DNMT3A* (n=12), *TP53* (n=11), *TET2* (N=9), *ASXL1* (n=7), and *RAS* (n=7). 35 pts are evaluable for response: 6 (18%) achieved complete remission (CR)/ complete remission with insufficient recovery of counts (CRI) (3 CR, 3 CRI), 5 (15%) had hematologic improvement (HI), 9 (26%) had ≥50% BM blast reduction, 3 pts (9%) had stable disease > 6 months, and 12 (34%) had progression. 16 pts are early for response assessment (<3 courses). The median number of courses to CR/CRI/HI was 3 (1 – 9). The CR/CRI/HI

(n=11) have been durable with no relapses among pts who achieved CR/CRI/HI [CR duration; not reached (NR)]. The 4- and 8-week mortality were 0 and 6%, respectively. The median overall survival for the 35 evaluable pts was 9.3 months (range, 1.8 – 14.3) (Fig 1) and this compares favorably to historical survival with AZA-based salvage protocols in similar pts treated at MDACC.

Grade 3/4 and Grade 2 immune mediated toxicities were observed in 7 (14%) and 6 (12%) pts, respectively. These included 8 episodes of pneumonitis, 2 nephritis, 2 transaminitis, and 1 skin rash. 1 pt died from grade 4 pneumonitis/epiglottitis. In the remaining 12 cases the toxicities responded rapidly to steroids and all 12 pts were successfully rechallenged with nivolumab. Time to onset of toxicities ranged from 4 days to 3.5 months. Four pts were postSCT and one had a grade 3 flare of GVHD of the skin and gut.

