Cohort 2 of azacitidine with nivolumab and ipilimumab enrolled 6 patients at the dose level 0 in Table 5B (i.e. azacitidine 75mg/m2 D1-7 with Nivolumab 3mg/kg Q2weeks and Ipilimumab 1mg/kg Q12 weeks). These patients were observed for the DLT period (28 days) and no DLTs were encountered among the first 6 patients treated at dose level 0. Subsequently, in accordance with Table 5B the dose level +1 was evaluated (i.e. azacitidine 75mg/m2 D1-7 with Nivolumab 3mg/kg Q2weeks and Ipilimumab 1mg/kg Q6 weeks). These patients were observed for the DLT period (28 days) and no DLTs were encountered among the first 6 patients treated at dose level +1. The RP2D was

selected as dose +1 (i.e, with ipilimumab Q6 weeks) and study opened to expansion with 24 additional patients to be enrolled in expansion using the dose level +1.

As of 08/01/2019 (Daver N et al, ASH 2019 Oral abstract #830: attached as Appendix), 31 R/R AML patients have been treated with Aza+Nivo+Ipi at all dose levels (dose level 0 = 6 patients, dose level +1 = 6 patients, and expansion at RP2D= 19 patients). Median age 71 years (26-86), secondary AML (49%), ELN unfavorable cytogenetics (65%), TP53 mutated (38%), median of salvage 2 (range, 1-4) status. 54% of the patients had previously received hypomethylating agent (azacitidine or decitabine)-based therapies either as single agent or in combination approaches. 4 patients had undergone prior allogeneic stem cell transplant (median time from allogeneic stem cell transplant of 13 months).

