24 patients were evaluable for response and survival, 7 too early (<3 months from start of therapy on protocol). CR/CRi was noted in 9 (36%), additionally 2 (8%) had hematologic improvement in one or more parameter (HI) maintained >6 months, 4 (16%) stable disease (SD) (defined as absence of CR, CRi, PR, MLFS; with stable disease on treatment for at least 6 months), and 10 (40%) were non-responders (NRs). Definitions of CR, CRi, PR, MLFS, stable disease were as per ELN 2017 response criteria. The 4-week and 8-week mortality were 0 and 8%, respectively, in this salvage population. In all salvage setting the median OS in Aza+Ipi+Nivo (n=24) versus Aza+Nivo (n=70) versus contemporary historical HMA-based clinical trial in R/R AML at MDACC (n=172), were 10.5, 6.4, and 4.6 months, respectively (p=0.0025) (Figure 1). This median OS with Aza+Ipi+Nivo compares favorably even to DAC10+venetoclax in R/R AML (med OS: 7.1 months) that will be reported from our center in a similar salvage population at ASH 2019 (Maiti A et al, ASH 2019). The 1-year OS in R/R AML pts with AZA+Nivo+Ipi was encouraging at 45%. The ORR and CR/CRi rates were also higher with AZA+Nivo+Ipi compared with AZA+Nivo and historical HMA-based controls. Grade 3/4 immune mediated toxicities were observed in 6 pts (25%), including rash, pneumonitis, and colitis. One pt required ICU stay but no deaths were attributed to immune toxicity. Other grade >2 toxicities were as expected for R/R AML population and were mostly infections/febrile neutropenia, and electrolyte disturbance. The 4-week mortality was 0, 8-week mortality was 8% and no deaths were attributed to immune related adverse events among the 24 evaluable patients treated with azacitidine with nivolumab and ipilimumab.

[figure not shown]

Figure 1: Median OS in AZA+Nivo+IPI (10.5 months) versus AZA+Nivo (6.4 months) versus HMA-based contemporary controls (4.6 months) treated on clinical trials at MDACC between 2011-2018

Table 1: Response and early mortality rates

| Best response | N (%) ; Median [Range] | | |
|---|------------------------|---------------------|------------------|
| | Aza+Nivo N=70 | Aza+Ipi+Nivo =24 | Control N=172 |
| Overall Response Rate | 23 (33) | 11 (46) | 35 (20) |
| CR | 4 (6) | 1 (4) | 17 (10) |
| CRi/CRp | 11 (16) | 7 (29) | 15 (9) |
| PR | 1 (1) | 0 | 1 (1) |
| HI* (6 months+) | 7 (10) | 2 (8) | 2 (1) |
| Stable disease (6 months+) [@] | 8 (11) | 4 (17) | NA |
| Non responders | 39 (58) | 8 (33) | 131 (76) |

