- During cycle 1, venetoclax will be dose escalated daily to the goal dose of 400mg daily. Patients will receive 100mg on Day 1, 200mg on Day 2 and 400mg on Day 3 and onwards, or adjusted dose if on concomitant azoles (discussed below in section 6.3). Venetoclax dose ramp-up as described in section 6.4.
- If venetoclax is not available at the start of therapy due to different reasons (insurance, financial, transportation, others), azacitidine and nivolumab can start and venetoclax is added when it becomes available.
- If azacitidine cycles are delayed, venetoclax therapy may continue on Days 1-21 of a 4-week cycle after discussion with the PI or Co-PI and documentation in the medical record. If azacitidine cycles are delayed, nivolumab may continue as scheduled (q2 weeks) after discussion with the PI or Co-PI and documentation in the medical record.

5.2.2 One cycle of therapy is defined as 28 days. Patients will receive one cycle of therapy every 28 days (+/- 7 days). The ipilimumab will be given every 6 weeks (+/-3 days).

5.2.2.1 In the expansion (part b) portion of the study (once the MTD/RP2D dose has been defined) cycles may be started early (but not earlier than day 21) for patients with active disease if judged in the best interest of the patient.

Nivolumab and azacytidine

For the lead-in (part a) cohort, DLT defining period is 28 days. As such, cycle 2 should not be started before 28 days for the patients being treated on the lead-in cohort.

5.2.2.2 Subsequent cycles may be delayed for recovery of toxicity or other medical conditions (e.g. infections). Delays in start of subsequent cycles greater than 8 weeks will be acceptable only for patients who are deriving clinical benefit and after discussion with the principal investigator of potential risk/benefit ratio.

5.2.2.3 In instances where one drug has to be discontinued transiently because of safety, the administration of the other drug may continue as scheduled. If the drug that is held can resume at a later time, no doses will be made up and the administration will follow the originally defined schedule calendar according to the drug that was continued.

5.2.2.4 Subsequent courses of 5-azacytidine and nivolumab OR 5-azacytidine with nivolumab and ipilimumab OR 5-azacytidine with nivolumab and venetoclax may be administered regardless of peripheral blood counts during the first 4 cycles and/or in the presence of residual leukemia.

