If prolonged myelosuppression (more than 8 weeks) WITH evidence of a hypocellular marrow (marrow cellularity less than 5% without evidence of leukemia) is observed, 5-azacytidine and nivolumab OR 5-azacytidine with nivolumab and ipilimumab OR 5-azacytidine with nivolumab and venetoclax will be discontinued. Delays in start of subsequent cycles greater than 8 weeks will be acceptable only for patients who are deriving clinical benefit and after discussion with the principal investigator of potential risk/benefit ratio. If the peripheral counts do not recover (ANC <1 x10⁹/L and/or platelets <30 x10⁹/L) but there is evidence of residual leukemia in the bone marrow by morphology or flow-cytometry, subsequent cycles can be administered at the discretion of the treating physician not earlier than 21 days after the prior cycle.

5.2.2.5 For patients who discontinue therapy, the reason for treatment discontinuation will be captured.

5.2.2.6 Patients must receive at least 5 of 7 planned doses of azacitidine, 2 of 2 planned doses of nivolumab and 18 of 21 planned doses of venetoclax during the first 28 days on trial (i.e. during cycle 1) to be considered evaluable

Nivolumab and azacytidine during the DLT phase. Patients who receive less than these doses of each drug during the first 28 days on trial will not be considered evaluable during the DLT phase. However, if such patients develop a toxicity that would normally be considered a DLT this will still be captured as a DLT. Any toxicity that meets the criteria for DLT during the first 28 days of trial in a patient who has received at least one dose of either azacitidine, venetoclax or nivolumab will constitute a DLT. Patients not considered evaluable due to insufficient dosing and who do not develop a toxicity that is considered a DLT will be replaced. These patients may continue therapy on trial after discussion with the PI if they are having clinical benefit and the reasons for continuation and potential benefit/risk profile for the patient must be clearly documented in the medical records. In the expansion phase (part b), DLT will not be monitored. We will perform continuous safety monitoring every 5 patients for “drug-related non-hematological Grade 3/4 AE’s.”

5.2.2.7 Dose modifications other than the ones mentioned above can be considered after discussion with the PI and proper documentation of the rationale.

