10 ADVERSE EVENT REPORTING

10.1 Adverse event is any untoward medical occurrence that may present during treatment with a pharmaceutical product but which does not necessarily have a causal relationship with this treatment.

Adverse drug reaction is a response to a drug which is noxious and unintended and which occurs at doses normally used in man for prophylaxis, diagnosis, or therapy of disease or for the modification of physiologic function.

Assessing causal connections between agents and disease is fundamental to the understanding of adverse drug reactions. In general, a drug may be considered a contributory cause of an adverse event if, had the drug not been administered, 1) the event would not have happened at all, 2) the event would have occurred later than it actually did, or 3) the event would have been less severe.

The Investigator or physician designee is responsible for verifying and providing source documentation for all adverse events and assigning the attribution for each event for all subjects enrolled on the trial.

10.2 Adverse Events (AEs) will be evaluated according to the latest CTC version 4 (Appendix C) and documented in medical record. Only unexpected AEs will be recorded in the Case Report Form (CRF). Expected events during leukemia therapy are:

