- Unless otherwise noted, the electronic SAE application (eSAE) will be utilized for safety reporting to the IND Office and MDACC IRB.
- Serious adverse events will be captured from the time of the first protocol-specific intervention, until 30 days after the last dose of drug, unless the participant withdraws consent. Additionally, any serious adverse events that occur between Day 31-100 will be captured as immune mediated toxicities from checkpoint inhibitors may have delayed manifestations. Serious adverse events must be followed until clinical recovery is complete and laboratory tests have returned to baseline, progression of the event has stabilized, or there has been acceptable resolution of the event.
- Additionally, any serious adverse events that occur after the 30 day time period that are related to the study treatment must be reported to the IND Office. This may include the development of a secondary malignancy.

Reporting to FDA:

- Serious adverse events will be forwarded to FDA by the IND Sponsor (Safety Project Manager IND Office) according to 21 CFR 312.32.

It is the responsibility of the PI and the research team to ensure serious adverse events are reported according to the Code of Federal Regulations, Good Clinical Practices, the protocol guidelines, the sponsor's guidelines, and Institutional Review Board policy

10.5 Serious Adverse event Reporting to Bristol-Myers Squibb Inc.

All Serious Adverse Events must be reported to BMS Worldwide Safety

- All SAEs, whether related or unrelated to nivolumab and all pregnancies must be reported to BMS (by the investigator or designee) within 24 hours.
- All SAEs should be reported via confirmed facsimile (fax) transmission, or scanned and reported via electronic mail to:
SAE Email Address: [contact]
SAE [contact]

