11.2 Sample Size

Arm 1:***Part a. Lead-in phase***

The primary objective of the lead-in phase is to determine the safety of nivolumab in combination with 5-azacytidine in patients with refractory/ relapsed AML. Up to 30 patients will be accrued into the lead-in part of the study.

Part b. Expansion phase

- A. Up to 70 patients (including 6 patients treated at the MTD from the lead-in part) with relapsed/refractory AML will be recruited for the Arm 1 Salvage cohort .
- B. Up to 40 newly diagnosed older AML patients (age ≥ 65) will be recruited for the Arm 1 Frontline older cohort .

Arm 2:**Part a. Lead-in phase**

The primary objective of the lead-in phase is to determine the safety of nivolumab with ipilimumab in combination with 5-azacytidine in patients with refractory/ relapsed AML. Up to 24 patients will be accrued into the lead-in part of the study.

Part b. Expansion phase

- A. Up to 54 patients (including 6 patients treated at the MTD from the lead-in part) with relapsed/refractory AML will be recruited for the Arm 2 Salvage cohort.
- B. Up to 30 newly diagnosed older AML patients (age ≥ 65) will be recruited for the Arm 2 Frontline older cohort.

The efficacy of the combination will be measured by the overall response rate (ORR), defined as CR (complete remission) + CR_p (complete remission with incomplete platelet recovery) + CR_i (complete remission with incomplete count recovery) + PR (partial response) + marrow clearance of blasts + hematologic improvement (HI) in platelets, hemoglobin, or ANC within 3 months of treatment initiation among adult patients with refractory/ relapsed AML AND newly diagnosed older patients with AML. ORR and toxicity will be monitored simultaneously using the Bayesian approach of Thall, Simon, Estey (1995, 1996) and the extension by Thall and Sung (1998).

Arm 3:**Part a. Lead-in phase**

The primary objective of the lead-in phase is to determine the safety of nivolumab with 5-azacytidine and venetoclax in patients with refractory/ relapsed AML. A total of 18 patients (3 dose levels with a maximum of 6 patients at each dose level) will be accrued into the lead-in part of the study.

Part b. Expansion phase

- A. A total of 30 patients (excluding 6 patients treated at the MTD from the lead-in part) with relapsed/refractory AML will be recruited for the Arm 3Salvage cohort.
- B. A total of 30 newly diagnosed older AML patients (age ≥ 65) will be recruited for the Arm 3 Frontline older cohort.

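### Arm 2 dose levels 0 and +1 are the same scheduled treatment through day 28, so the 28-day DLT rule makes level +1 the MTD without testing 6-weekly ipilimumab

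*Combined protocol and SAP*

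**What the plan says.** Primary objective 2 of the lead-in (section 1.1) is to find the MTD of azacitidine, nivolumab and ipilimumab. Table 5B starts at level 0 (ipilimumab 1.0 mg/kg every 12 weeks) and targets level +1 (1.0 mg/kg every 6 weeks). Azacitidine is 75 mg/m² and nivolumab 3.0 mg/kg at both levels. Section 5.2.1 places the first ipilimumab infusion on day 1 and later ones every 6 or 12 weeks, with a window of 3 days either way.

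On the observation period, section 5.2.2.1 says "For the lead-in (part a) cohort, DLT defining period is 28 days". Sections 5.2.1.6 and 11.3 define the MTD as the highest level with fewer than 2 of 6 patients having a DLT in the first 28 days. Section 5.2.2.8 applies the run-in MTD to both the salvage and the frontline cohorts.

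Section 2.3 D reports no DLTs in the first six patients at level 0, then that "no DLTs were encountered among the first 6 patients treated at dose level +1", and names level +1 as the RP2D. With longer follow-up of 24 evaluable patients across both levels, "Grade 3/4 immune mediated toxicities were observed in 6 pts (25%), including rash, pneumonitis, and colitis". No deaths were attributed to immune toxicity.

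The protocol recognises late immune toxicity elsewhere. For Arm 1, section 2.3 C notes: "Time to onset of toxicities ranged from 4 days to 3.5 months". Section 10.4 adds that "any serious adverse events that occur between Day 31-100 will be captured as immune mediated toxicities from checkpoint inhibitors may have delayed manifestations".

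**The concern.** Moving from level 0 to level +1 is meant to test more frequent ipilimumab. A dose-finding rule can test a change only if the change happens while toxicity is being counted. Here the counting stops before the two schedules diverge, so the second cohort of six repeats the first as far as the rule can see.

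What is at stake is the conclusion drawn for primary objective 2. A report stating that 6-weekly ipilimumab is the MTD on the strength of 0/6 DLTs would make a claim that toxicity from the 6-weekly schedule could not have contradicted.

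**Working it through.** The plan states no operating characteristic for the lead-in rule, so there is no figure of its own to reproduce. The check is on the calendar first, then on the rule.

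**1. When the levels diverge** (Table 5B, section 5.2.1)

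| | Level 0 | Level +1 |
|---|---|---|
| Azacitidine, mg/m² | 75 | 75 |
| Nivolumab, mg/kg | 3.0 | 3.0 |
| First ipilimumab, 1.0 mg/kg | day 1 | day 1 |
| Second ipilimumab, 1.0 mg/kg | 1 + 84 = day 85 (82 to 88) | 1 + 42 = day 43 (40 to 46) |

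No lead-in patient at either level was due a second infusion by day 28. The DLT definition below Table 5C speaks of the first cycle. With the 7-day allowance in section 5.2.2, that is 28 + 7 = 35 days, still before day 40.

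**2. The one longer window.** Haematologic DLT requires cytopenia with a hypocellular marrow lasting 42 days or more from cycle 1 day 1. An infusion given on day 40 at the earliest cannot have caused that. Section 5.3.1 also says that nivolumab and ipilimumab have not been linked to neutropenia or thrombocytopenia.

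**3. What the rule can detect.** Let p be the 28-day DLT probability, common to both levels because the treatment is common. A level passes with probability

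P(X ≤ 1) = (1 − p)^6 + 6p(1 − p)^5.

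- p = 0.10: 0.5314 + 0.3543 = 0.886
- p = 0.20: 0.2621 + 0.3932 = 0.655
- p = 0.30: 0.1176 + 0.3025 = 0.420

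Nothing in the formula depends on the ipilimumab interval. As an illustration with assumed rates, take p = 0.10 and let the second infusion add a later risk of 0%, 20% or 40% in patients without an early DLT. The total risk is then 10%, 1 − 0.9 × 0.8 = 28%, or 1 − 0.9 × 0.6 = 46%. The pass probability is 0.886 in all three cases.

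**4. What the lead-in data do show.** If the two successive cohorts are comparable, they give 0/12 DLTs on one common 28-day regimen. The one-sided 95% upper limit is 1 − 0.05^(1/12) = 22.1%. For a single 0/6 it is 1 − 0.05^(1/6) = 39.3%.

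**5. What the longer follow-up shows.** The 6/24 = 25% in section 2.3 D is not split by level or by timing. Six patients started at level 0, so at least 24 − 6 = 18 of the 24 were at level +1. The level +1 share lies between 0/18 and 6/18 (33.3%) if all six level 0 patients are among the 24, and is 6/24 if none are.

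**6. Whether better evidence is available.** Two of the 24 died by week 8, so at least 18 − 2 = 16 level +1 patients were alive at day 56, after the latest in-window second infusion (day 46). The number who received that infusion is not reported.

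**The case against.** The strongest reply is that nothing is hidden and later dosing is watched. Section 2.3 D gives the 28-day period and calls level +1 the RP2D, not the MTD. The salvage expansion is described as "Up to 54 patients (including 6 patients treated at the MTD from the lead-in part"), so the patients monitored under Table 15 are at level +1. That toxicity rule is applied every 6 patients and is not limited to 28 days. Table 18 does the same job for the Arm 2 frontline cohort. Section 11.3 also requires an efficacy and safety summary for IND Office review after the first 5 evaluable patients per cohort complete 3 months of treatment, and after every 5 thereafter. Three months is well past day 46. SAEs are captured to 30 days after the last dose, and then from day 31 to day 100.

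All of this stands, and it limits the point. It does not remove it: these safeguards are not the MTD rule, and none of them separates toxicity after the second infusion from toxicity before it. Sections 5.2.1.6 and 5.2.2.8 still attach the MTD label to the 28-day result.

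A reader might infer that 6-weekly ipilimumab is unsafe, or that the 25% grade 3/4 immune toxicity contradicts the clean lead-in. The documents support neither. The 25% is not a DLT rate and comes from longer follow-up over both levels. The 6 events in 24 concern immune toxicity only, while the Table 15 boundary is 12 in 24 for all drug-related grade 3/4 toxicity.

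**Conclusion.** The point holds as a limit on what may be concluded, and it is minor. Level +1 is the MTD by the protocol's definition, but that result carries no information on 6-weekly against 12-weekly ipilimumab. The lead-in supports a statement on first-cycle safety of one ipilimumab infusion with azacitidine and nivolumab: 0/12 DLTs, upper limit 22.1%, assuming comparable cohorts.

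The identity of the two levels through day 28 follows from the written schedule alone. The pass probabilities rest on assumed DLT rates and independent patients; their equality across levels rests on the shared schedule and comparable patients.

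It would go too far to say that level +1 was wrongly chosen or went unmonitored. The choice of RP2D may stand on other grounds, and no dose or enrolment decision needs to change.

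**What to change.** 1. In the Arm 2 report, state that levels 0 and +1 are identical through day 28, so the 28-day data describe first-cycle safety and do not establish 6-weekly ipilimumab as the MTD. Keep level +1 as the RP2D and give the basis for it. The report may quote 0/12 with its upper limit and the comparability assumption; that pooled figure does not belong in the protocol's design sections. Put the statement on the two levels into sections 5.2.1.6 and 11.3 when the protocol is next amended.
2. Rest the tolerability statement for 6-weekly ipilimumab on level +1 patients. Report drug-related grade 3/4 toxicity and SAEs through at least 30 days after the actual second infusion (day 43 + 30 = 73, or day 46 + 30 = 76 at the end of the window), with the number who received it.

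The cost is small. Level +1 salvage toxicity is already counted for Table 15, and section 10.3 puts all SAEs in the AE log and CRF, so this needs only a little extra tabulation. Starting with the report avoids an amendment for this alone, which section 12.0 would send through principal investigator, sponsor and IRB. The downsides are a less favourable MTD statement and a group small enough that it can describe tolerability but not compare schedules.
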